1.3.3. Exploratory

The incidence of PD-L1 expression on tumor cells and microglia/macrophages within the tumor will be determined and correlated to OS and PFS and other iRANO endpoints

The histological immunoscore will be determined and tested for association with OS, PFS, and other iRANO endpoints using logistic regression.

The association between 12 months OS and PFS with baseline neurocognitive function as measured by the evoked potential P300 (normal), the baseline corticosteroid dose, the average daily corticosteroid dose over the whole study duration, the extent to which patients complete the full 6 cycles of temozolomide based on temozolomide toxicity and the incidence and severity of treatment related irAE's will be tested using logistic regression.

The change if any in histological markers on tissue obtained from repeat resection

The estimation of the time period in which radiological progression was seen in clinically stable patients whose imaging was subsequently followed by radiological stabilization or regression

The estimation of the time period in clinically stable patients before radiological evidence of tumor regression occurred

The change in P300 will be determined and correlated with clinical outcomes as per iRAN

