### **5.3. Exploratory**

The correlation between OS and PFS and the prevalence of PD-L1 expression on tumor cells and microglia/macrophages within the tumor, the histological immunoscore.

The correlation between OS and PFS and the baseline corticosteroid dose, the total cumulative corticosteroid dose over the whole study duration, the total cumulative dose of temozolomide since diagnosis, the baseline value and the change from baseline to week 52 visit and/or the end of study neurocognitive function as measured by the evoked potential P300 and the incidence and severity of irAE's.

The change between baseline biomarker results and those obtained from biomarkers in tissue samples from patients with second surgical resection i.e. treatment failures

The description of the time period in which radiological progression was seen in clinically stable patients whose imaging was subsequently followed by radiological stabilization or regression

The description of the time period in clinically stable patients before radiological evidence tumor regression occurred

The change in P300 evoked potential values and its correlation with clinical outcomes

**Safety monitoring:** There will be an internal DSMB which will make annual reviews.

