1. STATISTICAL STATEMENT AND ANALYTICAL PLAN

1.1. Sample Size Considerations

A convenience sample of thirty (30) patients is based on recruitment feasibility. This sample size will permit estimation of dichotomous outcome rates with margins of error of less than 18% (based on a significance level of 0.05) and estimation of continuous parameter means to within 0.36 standard deviations. This is an early stage study, so analysis will focus on descriptive statistics. Continuous parameters will be summarized by means and 95% confidence intervals or by medians and interquartile ranges, as appropriate. Dichotomous outcomes will be summarized with point estimates of the rate, as well as 95% confidence intervals. Time-to-event data will be summarized using Kaplan-Meier curves.

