1.3.2. Secondary Endpoints

Based on the results of Stupp *et al* (2005) (3), if avelumab had no effect then we would expect to see one-year overall survival and progression-free survival rates of 60% and 27%, respectively. We will conclude that we have preliminary evidence of benefit if either of our observed rates is significantly better based on a one-sided t-test at the 0.2 level of significance. With our projected sample of 30, this corresponds to concluding benefit if at least 21 patients survive to one-year or if at least 11 have survived without progression of disease.

Radiological tumor response will be graded according to the immunotherapy Response Assessment for Neuro-Oncology (iRANO)

Progression of Disease (PD) will be defined as a $\geq 25\%$ increase on the 12 month MRI or CT scan in the sum of the product of the biperpendicular diameters of enhancing disease; or new lesions; or substantial worsened T2/FLAIR; or significant clinical neurological decline unexplained by a change in medication or concurrent comorbidities. The SPD is the sum of the products of biperpendicular diameters of the measurable enhancing lesions (max 5 lesions).

Complete Response (CR) will be defined as the disappearance on the month 12 MRI or CT scan of all enhancing disease, no new lesions, with stable or improved T2/FLAIR; no more than physiological steroids; clinically stable or improved

Partial Response (PR) will be defined as a $\geq 50\%$ decrease on the month 12 MRI or CT scan in the sum of the product of the biperpendicular diameters of enhancing disease, no new lesions, stable or improved T2/FLAIR, stable (>2 months) or decreased steroid dose, clinically stable or improved

Stable Disease (SD) will be defined at 12 months when a patient do not qualify for complete response, partial response, or progressive disease, stable or improved T2/FLAIR; stable (>2 months) or decreased steroid dose, clinically stable or improved

Overall survival (OS) will be defined as the time from baseline to the date of death from any cause.

Objective Response Rate (ORR) will be defined the number of patients with either CR or PR divided by the total number of patients.

Progression Free Survival (PFS) will be defined as the time from baseline to documented PD or death from any cause.

Results will be stratified according to MGMT status, baseline age (>50 yrs), baseline Karnofsky performance score (score of 100), radical tumor resection vs biopsy, primary versus secondary GBM,

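### Exploratory associations with OS and PFS use logistic regression, at 12 months for most covariates, so survival follow-up after week 52 goes unused; Cox models would recover it, mainly for OS

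*SAP*

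**What the plan says.** SAP 1.3.3 and protocol 12.3.3 carry the same exploratory text, which treats the covariates in three ways.

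- Immunoscore: it "will be determined and tested for association with OS, PFS, and other iRANO endpoints using logistic regression". No time point is given.
- P300, corticosteroid dose, temozolomide completion and irAEs: the paragraph opens "The association between 12 months OS and PFS with baseline neurocognitive function as measured by the evoked potential P300 (normal" and names logistic regression. Here 12 months is explicit.
- PD-L1 expression: it is to be correlated with OS, PFS and the other iRANO endpoints. No model is named. Protocol 5.3 is equally general: "The correlation between OS and PFS and the prevalence of PD-L1 expression on tumor cells".

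SAP 1.3.2 defines OS and PFS as times from baseline. Protocol 5.2 provides for censoring of both. Protocol 9.3.7 has survival calls every 4 weeks until death or end of study, and protocol 4.1 sets a maximum duration of 260 weeks. SAP 1.2 repeats the complete analysis every 52 weeks once all patients have reached week 52 or their end-of-study visit. The only time-to-event method named is the Kaplan-Meier curve, as a summary (SAP 1.1). The sample is 30, and no power is claimed for the exploratory tests.

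**The concern.** The outcome is collected as a censored time but tested as a yes/no status. Three things follow.

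1. The immunoscore test is incompletely specified. Logistic regression needs a binary outcome, and no date is given at which OS or PFS becomes one.
2. For a baseline covariate, a 12-month logistic test gives the same answer at every analysis after all 12-month statuses are known. Up to four further years of survival data cannot change it.
3. There is no rule for a patient censored before month 12.

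At stake is the chance of seeing a real prognostic or predictive signal in a sample of 30. No trial decision depends on these tests.

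**Working it through.** **Inputs from the documents.** n = 30 (SAP 1.1). Expected "one-year overall survival and progression-free survival rates of 60% and 27%, respectively" (SAP 1.3.2). Two-year survival of 27% (protocol 1.1.1), used only to set the shape of the OS curve. Imaging every 3 to 4 months (protocol 9.3.5). The 0.05 level is stated only for the margin of error (SAP 1.1); it is applied here two-sided.

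**Assumed, because the documents give no figure.** Hazard ratios of 2 and 3; a 15/15 marker split; accrual that gives 52 to 156 weeks of follow-up, uniformly spread, at the first complete analysis; no dropout; proportional hazards.

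**1. The plan's own figures.** Margin of error: 1.96 × √(0.25/30) = 0.179, under the stated 18%. Precision of a mean: 1.96/√30 = 0.358 SD, as stated. Cut-offs at one-sided 0.2, exact binomial: P(≥21 of 30 | 0.60) = 0.176 against 0.291 for ≥20; P(≥11 of 30 | 0.27) = 0.161 against 0.276 for ≥10. All reproduce. None of them concerns the exploratory tests.

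**2. Events by month 12.** Deaths: 30 × (1 − 0.60) = 12. PFS events: 30 × (1 − 0.27) = 21.9. Most PFS information is in by then; most OS information is not.

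**3. OS curve.** Weibull, S(t) = exp(−(t/λ)^k). From 60% at week 52 and 27% at week 104, k = ln(1.309/0.511)/ln 2 = 1.36 and λ = 52/0.511^(1/1.36) ≈ 85 weeks. This gives about 20 to 21 deaths at the first complete analysis and about 29 if all patients are followed for 260 weeks. An exponential curve would give 0.60² = 36% at two years and 26 to 27 deaths by week 260.

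**4. Approximate OS power by formula.** Overall one-year survival is held at 60%. If x is survival in the low-risk half, x + x^HR = 1.20. HR 2 gives 70.4% against 49.6%; HR 3 gives 76% against 44%.

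- 12-month status, two proportions with 15 per group. HR 2: Φ((0.208 − 1.96 × 0.179)/0.175) = 21%. HR 3: Φ((0.32 − 1.96 × 0.179)/0.169) = 43%.
- Time to event, Φ(√d × ln HR/2 − 1.96). HR 2: d = 12, 22%; d = 20.5, 35%; d = 29, 46%. HR 3: d = 12, 48%; d = 20, 69%; d = 29, 84%.

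**5. Simulated OS power**, likelihood-ratio logistic test against log-rank test:

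| HR | Logistic, 12 months | Log-rank, data cut at week 52 | Log-rank, first complete analysis | Log-rank, 260 weeks |
|---|---|---|---|---|
| 2 | 20% | 21% | 34% | 45% |
| 3 | 45% | 45% | 68% | 81% |

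Repeat runs agree to within about 2 points, and type I error is near 5% for both tests. The second and third columns show that event times within the first year add almost nothing. The later columns show the value of later follow-up.

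**6. PFS at the first complete analysis.** Power rises from about 34% to 44% at HR 2 and from 66% to 79% at HR 3. With exponential times, 24-month accrual and a Cox likelihood-ratio test, the rises are smaller: 34% to 41% and 65% to 75%.

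**7. Less favourable cases.**

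- PFS, HR 2.5, 35% marker prevalence, 3-monthly imaging, 24-month accrual: logistic 52%, Cox 50% with 10% yearly dropout. Dropout was applied to the Cox analysis only, which disadvantages it.
- OS, 80/20 split with the larger group at higher risk, first complete analysis: 18% against 16% at HR 2 and 31% against 35% at HR 3. The logistic type I error is about 7% here, so part of its power is spurious. A clear gain appears only at 260 weeks.

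**The case against.** These are exploratory analyses in a convenience sample. The plan says it will focus on description, claims no power for them and rests no decision on them. Twelve months is also the trial's own benchmark for OS and PFS, so association with one-year status is a coherent question. Losses to OS follow-up before month 12 should be few, given four-weekly calls and the permitted use of public records. Even with Cox regression, power at hazard ratio 2 is only 34% to 45%. All of this stands, and it limits how much weight the point can bear. It does not explain leaving the later survival data out of the tests.

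A reader might infer more than the documents support, in four ways.

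- That Cox regression is more powerful even on first-year data, because logistic regression treats a death at week 2 and one at week 51 alike. For OS with a binary marker that costs almost nothing (20% against 21%; 45% against 45%).
- That PFS gains as much as OS. About 73% of patients are expected to have had a PFS event by month 12, so less remains to be gained.
- That every biomarker is tested at 12 months by logistic regression. The immunoscore sentence has no time point, and PD-L1 has no model at all.
- That logistic regression should go altogether. The immunoscore sentence also covers other iRANO endpoints, and for binary ones such as objective response it is suitable.

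**Conclusion.** The point holds as an inexpensive improvement to an exploratory analysis. For baseline markers and OS, a time-to-event model on full follow-up adds about 14 points of power at the first complete analysis and 25 at 260 weeks at hazard ratio 2, and 23 and 36 points at hazard ratio 3. These figures rest on an even split, the assumed hazard ratios and accrual, no dropout and proportional hazards. The 260-week figure further assumes that every patient is followed that long, whereas the protocol gives 260 weeks as a maximum.

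For PFS the gain at the first complete analysis is about 7 to 13 points in the even-split settings, and it can disappear with an uneven split, interval imaging and dropout. The missing immunoscore time point and PD-L1 model, and the absence of a rule for early censoring, are gaps whatever the power. It would go too far to say that the plan's logistic tests are invalid for baseline markers, or that Cox regression would make this trial adequately powered for moderate effects.

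**What to change.** In SAP 1.3.3 and protocol 12.3.3:

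- For OS and PFS, use Cox regression on all follow-up available at each analysis, with one baseline marker per model: immunoscore, P300, baseline corticosteroid dose and PD-L1. Use a Firth penalty where events are sparse, and check proportional hazards. Report hazard ratios with 95% confidence intervals as exploratory estimates.
- For average corticosteroid dose, temozolomide completion and irAEs, which arise after baseline, use landmark or time-dependent Cox models. Entered as fixed covariates they would bring immortal-time bias, because a patient must live long enough to acquire the value. The 12-month logistic model has a similar problem.
- Keep logistic regression for binary iRANO endpoints such as objective response.

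The cost is a wording change in two places, with no new visits or data. The downsides are that proportional hazards must be checked, landmark times must be chosen in advance, and 30 patients still give low power for moderate effects.

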The 21 subjects reporting Grade 4 treatment-related TEAEs experienced events of infusion-related reaction (3 subjects; 0.2%), blood CPK increased, GGT increased, hyperglycemia (2 subjects each; 0.2%), lipase increased, amylase increased, myositis, hypophosphatemia, hypokalemia, embolic stroke, frontal lobe epilepsy, monoplegia, syncope, dyspnea, pneumonitis, respiratory failure, anemia, neutropenia, thrombocytopenia, autoimmune neutropenia, sepsis, cardiac arrest (1 subject each; 0.1%), and 1 uncoded event. The 4 subjects with Grade 5 treatment-related TEAEs

experienced events of radiation pneumonitis, pneumonitis, respiratory distress and acute hepatic failure, autoimmune hepatitis (Grade 3) with consequent fatal liver failure. Infusion-related reactions including drug hypersensitivity reactions and immune-mediated adverse reactions have been identified as expected adverse drug reactions of avelumab. The safety profile of avelumab is consistent with findings reported for other anti-PD-1 or anti-PD-L1 antibodies.

Immune-related adverse event (irAEs) are considered AE's of special interest. Treatment-related potential irAEs were observed in 99 of 1300 subjects (7.6%) in the pooled expansion cohort. Hypothyroidism was the most frequent treatment-related potential irAE, which occurred in 45 subjects (3.5%) in the pooled expansion cohort. The other frequent potential irAEs, which were considered as treatment-related, were pneumonitis (13 subjects; 1.0%), hyperthyroidism (7 subjects; 0.5%), adrenal insufficiency and dry eye (5 subjects each; 0.4%), autoimmune hepatitis and colitis (4 subjects each; 0.3%), and myositis (3 subjects; 0.2%). Additional treatment-related potential irAEs were seen in 2 or 1 subjects in the pooled expansion cohort. The majority of potential irAEs were Grade 1 or Grade 2 events. In the pooled expansion cohort, potential irAEs  $\geq$  Grade 3 occurred in 29 (2.2%) subjects. Potential irAEs leading to death occurred in 3 (0.2%) subjects, which were all assessed as treatment-related events. In the pooled expansion cohort, 15 subjects (1.2%) had potential irAEs that led to trial treatment discontinuation. Overall, as of 05 November 2015, there were no treatment-related immune-mediated AEs reported in Trial EMR 100070-001 with onset after the on-treatment period, i.e., 30 days after the last drug administration.

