### **4.2. Treatment Phases of the Study**

**Combination Phase:** Upon completion of the standard combination therapy of radiotherapy (total dose 60 Gy, administered as daily 2Gy fractions, 5 days/week or as per local standard) and temozolomide (75 mg/m^2/day p.o. qd) and a treatment break of no more than 21 days, the combination phase will start. Patients will receive temozolomide and avelumab for 6 cycles of 28 days each. During the 1st cycle Temozolomide will be given the first 5 days at a dose of 150mg/m^2/day p.o. In the next cycle, the temozolomide dose should be escalated to 200/mg/m^2 if permitted by the patient's hematological and non-hematological toxicity profile (as per NCI-CTC AE version 5). The temozolomide dose will be adjusted according to hematological and non-hematological toxicity as per temozolomide's product monograph (appendix 4). Avelumab will be administered on day 1 and day 15 of each cycle at a dose of 10mg/kg IV. Avelumab therapy will be withheld according to the occurrence and severity of avelumab emergent adverse events as per table 3. Patients will continue the

combination of temozolomide (150 – 200mg/m^2 per day PO X5 days Q28days) and avelumab (at 10mg/kg dose, IV on days 1 and 15 per cycle) until 6 cycles are completed or until the occurrence of a termination event.

**Monotherapy Phase:** Upon completion of the Combination Phase or upon stopping temozolomide because of temozolomide related toxicity/tolerability issues or patient choice, the patient will continue into the avelumab Monotherapy Phase. Avelumab 10mg/kg IV Q2weeks will be continued as monotherapy until the occurrence of a termination event defined as one of the following: 1) clinical evidence of neurological deterioration resulting in an ECOG score of at least 3 or more, unexplained by other comorbidities, unchanged by an increase in corticosteroid dose and sustained for at least two weeks or 2) treatment emergent adverse event (TEAE) of grade 3 or more or 3) withdrawal of patient consent.

Patients who experience irAE's may according to table 3 directives have their avelumab therapy suspended.

The use of Bevacizumab or re-irradiation will not be allowed in the study and will be considered as evidence of a termination event.

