## **10. INVESTIGATIONAL MEDICINAL PRODUCT**

### **10.1. Dose and Schedule of Test Drug**

Avelumab is a fully human IgG1 antibody directed against PD-L1. Avelumab binds PD-L1 and blocks the interaction between PD-L1 and its receptors PD-1 and B7.1. This removes the suppressive effects of PD-L1 on anti-tumor CD8+ T cells, resulting in the restoration of cytotoxic T cell response.

Avelumab will be administered intravenously every 14 days starting the same day as the first day of the first 5 days po temozolomide treatment. Temozolomide's 28 days cycle will be repeated 6 times or until grade 3 or higher temozolomide related treatment AE's. Avelumab will be continued IV q14 days for 260 weeks or until grade 3 or higher avelumab treatment-related AE's occurs and independent of whether the patient continues or completes the 6 cycles of temozolomide.

Avelumab may be withheld temporarily in the case of irAE according to the irAE's algorythms (table 3)

Temozolomide dose may be adjusted or withheld according to the directives in the temozolomide's product monograph (appendix 4)

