## Assessment and Initial Management of Tumor Lysis Syndrome

## 11.6. Immune related Adverse Event (irAE)

Immune checkpoint inhibitors are known to cause autoimmune adverse events. Previous studies with avelumab has shown an incidence of 9.7% most of them of grade 2 severity.

Any untoward medical occurrence, sign/symptom, disease, including laboratory abnormality or exacerbation of previous condition occurring during the study drug and believed to be of autoimmune origin will be classified as an immune related/emergent autoimmune adverse event (irAE).

Treatment of irAE's is mainly dependent upon severity (NCI-CTCAE grade):

Grade 1 to 2: treat symptomatically or with moderate dose steroids, more frequent monitoring

Grade 1 to 2 (persistent): manage similar to high grade AE (Grade 3 to 4)

Grade 3 to 4: treat with high dose corticosteroids

Treatment of irAEs should follow guidelines set forth in the table below (table 3).

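### Immune-related events, temozolomide completion and on-study steroid dose arise after baseline, so the planned 12-month logistic regressions on them give biased exploratory odds ratios

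*SAP*

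**What the plan says.** SAP 1.3.3 and Protocol 12.3.3 name 12-month OS and PFS as outcomes and logistic regression as the method. Two predictors are known at baseline (P300 and baseline steroid dose). Three are not:

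- steroid exposure, as "the average daily corticosteroid dose over the whole study duration";
- temozolomide, as "the extent to which patients complete the full 6 cycles of temozolomide based on temozolomide toxicity";
- irAEs: "the incidence and severity of treatment related irAE's will be tested using logistic regression".

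Neither document gives a counting window, a landmark, a time-dependent step, or a rule for patients who die or progress before they could have an irAE or reach cycle 6.

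On stopping temozolomide, Protocol 10.1 says "Temozolomide's 28 days cycle will be repeated 6 times or until grade 3 or higher temozolomide related treatment AE's". Protocol 4.2 also provides for "upon stopping temozolomide because of temozolomide related toxicity/tolerability issues or patient choice" and for termination events, and Protocol 6.2 lists progressive disease among the reasons to discontinue study treatment.

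The exposure variables differ between sections. The synopsis (exploratory objectives, exploratory endpoints, tertiary endpoints) and Protocol 3.3 and 5.3 use cumulative steroid and cumulative temozolomide dose. Protocol 12.3.3 and SAP 1.3.3 use average daily steroid dose and cycle completion.

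**The concern.** A logistic model of 12-month status treats each predictor as if it were known at time zero. These three are not, and the outcome itself limits how much of each can be observed.

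- **irAEs.** A patient who dies at month 3 has three months in which to have one; a survivor has twelve or more.
- **Temozolomide.** The last dose of cycle 6 falls on day 5 x 28 + 5 = 145. A patient who dies before then cannot complete. Whether that patient is a non-completer is not stated.
- **Steroids.** Dose can rise as a patient deteriorates, and a whole-study average includes doses taken after the 12-month outcome is already fixed. Cumulative dose grows with survival time even when daily dose is constant.

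Relating irAEs and drug exposure to OS and PFS is a stated exploratory objective. A finding that patients with irAEs, or patients who completed temozolomide, lived longer could come entirely from this structure. More patients would not remove the bias; they would estimate the wrong quantity more precisely.

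**Working it through.** **Inputs from the documents.** n = 30; one-year OS 60% and PFS 27% (SAP 1.3.2); two-year survival 27% (Protocol 1.1.1); irAE incidence 99/1300 = 7.6% (Protocol 2) or 9.7% (Protocol 11.6: "Previous studies with avelumab has shown an incidence of 9.7% most of them of grade 2 severity"), so 30 x 0.076 = 2.3 to 30 x 0.097 = 2.9 patients.

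**Assumptions.** The documents give neither irAE onset times nor temozolomide stop rates. I take constant irAE and toxicity hazards and vary the window, and 10-30% toxicity stops by day 145. No predictor affects survival, so every true odds ratio is 1.

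**Plan's own figures.** The 21/30 and 11/30 thresholds reproduce. Exact one-sided p is 0.176 for 21 (0.291 for 20) against 60%, and 0.161 for 11 (0.276 for 10) against 27%. They use none of the three predictors.

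**OS curve.** Weibull through 60% at 12 and 27% at 24 months: shape = ln[ln(0.27)/ln(0.60)]/ln 2 = 1.358.

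**irAEs and OS**

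1. Mean time to death among those who die by month 12 = (integral of S from 0 to 12 - 12 x 0.60)/0.40 = (9.77 - 7.20)/0.40 = 6.43 months. Survivors have 12, so with a low constant hazard the risk ratio is about 12/6.43 = 1.87.
2. At 9.7% overall by month 12, the risk is 11.85% in survivors and 6.48% in those who die. Odds ratio = (0.1185/0.8815)/(0.0648/0.9352) = 1.94. At 7.6% it is 1.92.
3. Counted over 60 months, 9.7% overall splits into 13.72% and 3.68%. Odds ratio = (0.1372/0.8628)/(0.0368/0.9632) = 4.2; at 7.6% it is 4.1.
4. With onset confined to the first 12 or 24 weeks: 1.1 or 1.2.

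For PFS with a 12-month window, an exponential progression model gave 1.3-1.4. At n = 30, false positives for irAEs by month 12 rise little: under 1% by Wald or Fisher and 5-9% by likelihood-ratio test, at nominal 5%. In 44-66% of simulated trials no finite odds ratio exists. For severity, Protocol 2 reports, for grade 3 or higher, "Grade 3 occurred in 29 (2.2%) subjects". Then 30 x 0.022 = 0.66 patients are expected, and the chance of none is 0.978^30 = 0.51.

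**Temozolomide completion and OS**

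1. S(day 145) = 0.864. Among those who die by month 12, the share alive at day 145 is r = (0.864 - 0.600)/0.400 = 0.661.
2. *Early death counts as non-completion.* With toxicity-stop rate q, odds ratio = [1 - (1 - q)r]/(q r). For q = 0.10: (1 - 0.595)/0.0661 = 6.1. For q = 0.30: (1 - 0.463)/0.198 = 2.7. Simulation gave 2.7-6.2.
3. *Only toxicity stops count.* For q = 0.10, toxicity stops occur in 10% of survivors but 8.56% of those who die, who had less time. Odds ratio = (0.90/0.10)/(0.9144/0.0856) = 0.84. For q = 0.30 it is 0.81.
4. *Progression also stops temozolomide* (PFS exponential with 27% at 12 months, then death at 0.121 per month): 4.7-6.7 with all-cause coding and 0.62-0.66 with toxicity-only coding. Fisher false positives under all-cause coding are 56% at q = 0.10 and 36% at q = 0.30, at nominal 5%.

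**Steroids.** Illustration only: baseline dose 3 mg/day (SD 1.5), rising by 4-8 mg after progression, odds ratios per SD.

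| Variable and window | OS | PFS |
|---|---|---|
| Average dose, 12 months | 0.54-0.62 | 0.09-0.27 |
| Average dose, 60 months | 0.95-0.96 | 0.32-0.47 |
| Cumulative dose, 12 months | 1.5-2.0 | 0.32-0.63 |

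If dose does not change at progression, average dose gives 1.0 for both outcomes, but cumulative dose over 12 months still gives 2.8 for OS.

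**Remedies under the null**

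- irAE week-24 landmark, OS: 0.99-1.01 if dosing continues after progression, about 1.3 if avelumab stops at progression.
- irAE as a time-dependent Cox covariate, OS: hazard ratio 1.01 if dosing continues, about 0.73 if avelumab stops at progression, 0.98 if then stratified by progression status.
- Temozolomide week-24 landmark, OS, if temozolomide stops at progression: 2.8-3.7 with all-cause coding, about 0.8 with toxicity-only coding.

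**The case against.** The strongest reply is that these analyses are exploratory, are called associations, carry no significance level or decision, and sit in a study that says it will focus on descriptive statistics. With two or three irAE patients expected, the irAE model will rarely reject anything. That stands, and it limits the seriousness. It does not make the odds ratios interpretable.

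Several stronger readings are tempting, and the documents do not support them:

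- *The direction of all three biases depends on coding.* Not for irAEs: every setting tried gave an odds ratio above 1, and only its size varied. Direction turns on coding for temozolomide, and on average versus cumulative dose for steroids and OS.
- *irAEs can be counted only during treatment.* The source trial had "no treatment-related immune-mediated AEs reported in Trial EMR 100070-001 with onset after the on-treatment period", but that period already ran to 30 days after the last dose. Protocol 4.2 also observes patients for delayed irAEs over a 90-day off-treatment phase.
- *Steroid dose is by definition part of PFS.* This rests on Protocol 8.4 alone. There, needing dexamethasone above 12 mg/day, or for longer than 7 days, for peritumoral edema counts as progression after the first three months. The definitions of progression in Protocol 5.2 and 12.3.2 and SAP 1.3.2 contain no such threshold.
- *The largest figures are what the plan will produce.* The wording on temozolomide toxicity leans towards toxicity-only coding, where the bias is modest. The 60-month irAE window is neither stated nor excluded.

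A landmark does restore a null temozolomide result if stopping is unrelated to progression. Because Protocol 6.2 lists progression as a reason to stop study treatment, that cannot be relied on.

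**Conclusion.** The concern holds, for exploratory results only. As written, the plan gives biased odds ratios for three post-baseline predictors. For irAEs and OS the bias is upward: about 1.9-2.0 to month 12, about 4.1 over 60 months, 1.1-1.2 with early onset. For temozolomide completion and OS it is about 2.7-6.2 or about 0.8 depending on coding, and 4.7-6.7 or 0.6-0.7 if progression also stops the drug. For steroids the problem is structural, and its size cannot be fixed from the documents. The odds-ratio sizes depend on the assumed survival curves, hazards and stop rates. That the odds ratios are biased does not, provided irAEs are not all very early and some patients die before cycle 6.

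A reader might infer that the trial's conclusion on benefit is compromised. It is not: the primary safety endpoint and the 21/30 and 11/30 rule do not use these variables, and the two baseline predictors do not share the problem.

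**What to change.** 1. **irAEs.** Replace the fixed predictor with a time-dependent covariate from onset date in a Cox model, or with a week-24 landmark that counts irAEs only up to week 24. State three limits: about 1-2 exposed patients are expected; some OS bias remains if avelumab stops at progression (landmark odds ratio about 1.3 under the null); and adjusting for progression status would also remove any effect that acts through progression. Report severity as counts.
2. **Temozolomide.** State how death, progression and patient choice before cycle 6 are coded. Report completion descriptively with reasons for stopping, and do not test it as a predictor of survival.
3. **Steroids.** Keep baseline dose as the predictor and report on-study dose descriptively. Use no cumulative dose, and no dose after the outcome date, as a fixed predictor. Reconcile the steroid rule in Protocol 8.4 with the progression definitions in Protocol 5.2 and 12.3.2 and SAP 1.3.2.
4. **Definitions.** Reconcile the steroid and temozolomide variables in the synopsis and Protocol 3.3 and 5.3 with Protocol 12.3.3 and SAP 1.3.3.

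**Cost.** SAP wording and little programming. Event onset dates (Protocol 11.13) and steroid doses with dates (Protocol 8.1) are already recorded; the reason for stopping temozolomide may need one CRF field. An OS landmark drops about 4-5 of 30 patients: 30 x (1 - 0.867) = 4.0 under the progression model and 30 x (1 - 0.837) = 4.9 under the Weibull curve. None of this makes 30 patients informative about irAEs; it removes or discloses a misleading estimate.
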